2.2 Analysis sets

Enrolled Set (ENR): The ENR will comprise all patients, who provided informed consent.

Randomized Analysis Set (RAS): The RAS is defined as all subjects who were randomized. Unless otherwise specified, misrandomized subjects will be excluded from the RAS. Misrandomized patients are defined as cases where subjects were mistakenly randomized by the investigator/qualified site staff either prematurely or inappropriately prior to confirmation of the subject's final randomization eligibility and double-blind treatment was not administered to the subject.

Full Analysis Set (FAS): The FAS comprises all subjects to whom study treatment/reference treatment has been assigned by randomization. According to the intent to treat principle, subjects will be analyzed according to the treatment they have been assigned to during the randomization procedure.

Safety Set: The Safety Set includes all subjects who received at least one dose of study treatment/reference treatment. Subjects will be analyzed according to the study treatment received, where treatment received is defined as the first dose of study/reference treatment.

2.2.1 Subgroup of interest

Interactions between treatment and selected Baseline demographics and disease characteristics will be explored for ASAS 40 response at Week 24. Subgroup analyses for the primary efficacy endpoint will be performed on the following based on the patient's Baseline status:

- Gender: (Male, Female).
- Age group (year): (≥ 18 to ≤ 64 , > 64 to ≤ 75 , > 75).
- Disease severity based on ASDAS at Baseline: (< 1.3 , ≥ 1.3 to < 2.1 , ≥ 2.1).
- CRP blood level at Baseline (mg/l): (≤ 5 , > 5).

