5.1 Inclusion criteria

Patients eligible for inclusion in this study must fulfill all of the following criteria:

1. Patient must be able to understand and communicate with the investigator and comply with the requirements of the study and must provide written, signed and dated informed consent before any study assessment is performed.
2. Male or non-pregnant, non-lactating female patients at least 18 years of age.
3. Diagnosis of axSpA (either r-axSpA (AS) or nr-axSpA) fulfilling the ASAS classification criteria for axSpA ([Appendix 2](#)).
4. Active disease as defined by having an ASDAS ≥ 2.1 at Screening and Baseline despite concurrent NSAID therapy, or intolerance/contraindication to NSAIDs.
5. Objective signs of inflammation at Screening as defined by:
MRI of sacroiliac joints performed up to 3 months prior to screening showing acute inflammatory lesion(s),
OR
elevated quick CRP (> 5 mg/L),
OR
MRI showing acute inflammatory lesion(s) in the sacroiliac joints performed during screening period.
6. Patients should have been on at least 2 different NSAIDs at the highest recommended dose for at least 4 weeks (in total) in the past, with an inadequate response or failure to respond, or less if therapy had to be reduced due to intolerance, toxicity or contraindications.
7. Patients who are regularly taking NSAIDs (including cyclooxygenase-1 [COX-1] or cyclooxygenase-2 [COX-2] inhibitors) as part of their axSpA therapy are required to be on a stable dose for at least 1 week before randomization.
8. Patients taking MTX (7.5 mg/week to 25 mg/week) or sulfasalazine (≤ 3 g/day) are allowed to continue their medication but are required to be on a stable dose for at least 4 weeks before randomization.
9. Patients who are on a DMARD other than methotrexate (MTX) or sulfasalazine must discontinue the DMARD 4 weeks prior to randomization.
10. Patients taking corticosteroids must be on a stable dose of ≤ 10 mg/day prednisone or equivalent for at least 2 weeks before randomization and should remain on a stable dose up to Week 24.

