16.1 Appendix 1: Clinically notable laboratory values

The following criteria will be used to define expanded limits and notable abnormalities of key laboratory tests.

Clinically notable values will be forwarded to Novartis/CRO at the same time that they are sent to investigators. Any action based on these laboratory values should be discussed with Novartis/CRO personnel.

Table 16-1 Safety analyses: expanded limits and notable criteria

Laboratory Variable	Final Harmonization	
	Notable Criteria	SI Units
	Standard Units	
LIVER FUNCTION AND RELATED VARIABLES		
SGOT (AST)	> 3 x ULN	> 3 x ULN
SGPT (ALT)	> 3 x ULN	> 3 x ULN
GGT		
Bilirubin	> 2 x ULN	> 2 x ULN
Alkaline phosphatase	> 2.5 x ULN	> 2.5 x ULN
RENAL FUNCTION, METABOLIC AND ELECTROLYTE VARIABLES		
Creatinine (serum)	> 2 x ULN	> 2 x ULN

16.2 Appendix 2: Assessment of spondyloarthritis international society criteria for axial spondyloarthritis

ASAS criteria for classification of axSpA will be applied as defined by [Sieper et al \(2009\)](#).

Diagnosis of axial spondyloarthritis according to the assessment of spondyloarthritis international society classification criteria

Diagnosis of axSpA (either AS or nr-axSpA) according to ASAS axSpA classification criteria to be applied in patients with back pain for at least 3 months and age of onset < 45 years:

- Sacroiliitis on imaging with ≥ 1 SpA feature **or**
- HLA-B27 positive with ≥ 2 SpA features

Sacroiliitis on imaging

- Active (acute) inflammation on MRI highly suggestive of sacroiliitis associated with SpA (see [Appendix 6](#))
- Definite radiographic sacroiliitis according to the modified New York diagnostic criteria (van der Linden et al 1984) (see [Appendix 5](#))

Spondyloarthritis features

- Inflammatory back pain
- Arthritis
- Enthesitis (heel)
- Uveitis
- Dactylitis
- Psoriasis
- Crohn's disease or colitis
- Good response to NSAIDs
- Family history for SpA
- HLA-B27
- Elevated CRP

Source: Sieper J, Rudwaleit M, Baraliakos X, et al (2009) The Assessment of SpondyloArthritis international Society (ASAS) handbook: a guide to assess spondyloarthritis. Ann Rheum Dis.; 68 Suppl 2:ii1-44

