2.5.4 Supportive analyses

Supportive analyses will be conducted in order to provide evidence that the results seen from the primary model are robust. Possible effect modification due to patient characteristics will be explored by subgroup analyses for sex (male, female), age class (≥ 18 to ≤ 64 , > 64 to ≤ 75 , > 75 years), disease severity based on ASDAS (< 1.3 , ≥ 1.3 to < 2.1 , ≥ 2.1) and CRP blood level

(≤ 5, > 5) (mg/L) at Baseline. The primary model may also be recalculated with these factors included as well as with the respective terms for a subgroup by treatment interaction.

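### The age bands split at 64 and 75 are likely to leave the upper classes too sparse for a useful ASAS40 subgroup or interaction estimate, and the SAP gives no merging rule

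*SAP*

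**What the plan says.** SAP 2.2.1 lists four Baseline factors for subgroup analysis of the primary endpoint: sex, age, ASDAS severity and CRP. The age entry, labelled "Age group (year", reads with its classes "Age group (year): (≥ 18 to ≤ 64 , > 64 to ≤ 75 , > 75". SAP 2.5.4 repeats it as "age class (≥ 18 to ≤ 64 , > 64 to ≤ 75 , > 75 years" and adds "The primary model may also be recalculated with these factors included as well as with the respective terms for a subgroup by treatment interaction". The subgroup work is described as exploratory.

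Protocol 12.4.4 names an age class but sets no cut-points, so 64 and 75 are the SAP's choice. SAP 2.3.3 uses the same bands in the demographic table.

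Two passages bear on who can enter:

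- **Age at entry.** Protocol 5.1 has only a lower limit: "Male or non-pregnant, non-lactating female patients at least 18 years of age".
- **Age at onset.** Protocol 5.1 also requires patients "fulfilling the ASAS classification criteria for axSpA". Appendix 2 (Section 16.2) applies those criteria to patients with "back pain for at least 3 months and age of onset < 45 years".

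Neither document gives an expected age distribution. The SAP has no minimum class size, no rule for merging sparse classes and no sparse-data method.

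**The concern.** Entry requires disease that began before 45. A patient over 75 would have had symptoms for more than 30 years, would never have received a TNF or IL-17 biologic (Protocol 5.2), and would still have active disease. Such patients can enter but should be uncommon. With 300 randomized, bands cut at 64 and 75 could put almost everyone in one class.

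The lowest band would then repeat the overall result. The upper bands would give odds ratios that are infinite, undefined or too wide to read. Age is one of only four pre-specified effect modifiers, and the planned analysis might say almost nothing about it. With no merging rule, any regrouping would be decided after the data are seen, in an open-label trial.

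**Working it through.** **Inputs from the documents.** N = 300, allocated 1:1; ASAS40 response 50% (T2T) and 30% (SOC) (Protocol 12.7.1, SAP Section 3); two-sided alpha 0.05 (SAP 2.5.2).

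**The plan's own figure.** No figure is given for the age subgroup. The sample size does reproduce:

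- Uncorrected: n' = [1.96√(2·0.4·0.6) + 1.2816√(0.25 + 0.21)]² / 0.2² = 124.0.
- Continuity-corrected: n = (n'/4)·[1 + √(1 + 4/(n'·0.2))]² = 133.8, so 134 per arm, as stated.

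**Step 1: expected class sizes.** The age distribution is an assumption: normal, truncated at 18, age in completed years. The bands are therefore below 65, 65 to below 76, and 76 or above on the exact scale.

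| Assumed mean, SD | 18 to 64 | >64 to 75 (of 300) | >75 (of 300) |
|---|---|---|---|
| 36, 10 | 99.8% | 0.6 | 0.01 |
| 40, 12 | 98.1% | 5.4 | 0.4 |
| 45, 13 | 93.7% | 16.3 | 2.6 |
| 48, 13 | 90.3% | 24.2 | 4.7 |

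**Step 2: chance that a class gives no finite odds ratio.** A finite value needs at least one responder and one non-responder in each arm. For a class of n patients, with a in T2T and b = n − a in SOC:

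P(no finite OR) = 1 − Σ Bin(a; n, ½)·(1 − 2·0.5^a)·(1 − 0.3^b − 0.7^b), where terms with a or b below 2 count as zero.

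For n = 5 only two splits contribute:

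- a = 2, b = 3: 0.3125·0.50·0.63 = 0.098
- a = 3, b = 2: 0.3125·0.75·0.42 = 0.098

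The result is 1 − 0.197 = 0.80.

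| Class size | 2 or 3 | 4 | 5 | 6 | 9 | 15 | 24 |
|---|---|---|---|---|---|---|---|
| P(no finite OR) | 1.00 | 0.92 | 0.80 | 0.68 | 0.38 | 0.12 | 0.02 |

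These figures ignore the center factor in the primary model, which would make matters worse.

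**Step 3: precision where the odds ratio is finite.** With m = n/2 per arm, SE(log OR) = √[(1/0.25 + 1/0.21)/m] = √(8.762/m).

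- n = 15: SE = √(8.762/7.5) = 1.08. The 95% CI is the OR multiplied and divided by exp(1.96·1.08) = 8.3. Power for 50% against 30% is 12%.
- n = 24: SE = √(8.762/12) = 0.85. The factor is 5.3 and power is 16%.

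**Step 4: interaction of that class against the rest.** SE = √(SE²class + SE²rest), and the ratio of odds ratios needed for 80% power is exp(2.8·SE).

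- n = 15, rest 285: √(1.081² + 0.248²) = 1.109, giving a ratio of about 22.
- n = 24, rest 276: √(0.854² + 0.252²) = 0.891, giving a ratio of about 12.

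**The case against.** A reader might infer that onset before 45 makes the upper bands nearly empty, so that the age subgroup cannot be estimated at all. The documents do not support that. The criterion limits age at onset, not age at entry. Protocol 5.1 has no upper limit, so patients with long-standing disease can enter at 65 or older. The sparsity rests on an age distribution that neither document gives. The 18 to 64 class is estimable, and a middle class of 15 to 24 patients usually gives a finite odds ratio, though a poor one. All of this stands.

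It also stands that the impact is limited. The subgroup work is exploratory, the interaction is optional, no claim or alpha attaches to it, and the primary model does not contain age.

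On the remedy, the objection is that a split at the median or at 40 years asks a different question from how the effect looks in older patients, depends on the data or has no source in the documents, and breaks the match with the demographic table. It would also come late, since the SAP is already at amendment 4.0 (July 2023). This is a fair case against new cut-points. It has much less force against a continuous term, which needs no cut-point and leaves the existing bands in the descriptive tables.

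What does not stand is the suggestion that nothing need change. Even the oldest distribution considered (mean 48, SD 13) expects about 5 patients over 75, and a class of 5 fails to give a finite odds ratio 80% of the time.

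**Conclusion.** The point holds as a minor, inexpensive improvement. Under assumed means of 36 to 48 years and SDs of 10 to 13, the over-75 odds ratio and the three-level interaction will probably not be estimable. The over 64 to 75 estimate will be very imprecise: even at 15 to 24 patients its 95% CI spans a factor of about 5 to 8 either side, and with 6 or fewer it usually has no finite value. The lowest band, with 90% to 99.8% of patients, will be close to the whole-trial result. As written, the age analysis can therefore say little about effect modification.

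The conclusion depends on the assumed ages. A materially older population would weaken it. The onset criterion makes older patients less common but does not by itself prove that the bands are sparse. The primary test and the sample size are unaffected.

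**What to change.** 1. In SAP 2.5.4, fit the age-by-treatment interaction with continuous Baseline age, and report the estimated treatment effect at a few ages named in advance.
2. Keep the 64 and 75 bands for the demographic table and for descriptive ASAS40 response counts by arm.
3. Merge the two upper bands into over 64 for any subgroup odds ratio, in both SAP 2.2.1 and SAP 2.5.4.

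A split at the median or at 40 years is a matter of preference and is not required.

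**Cost.** SAP wording only: Protocol 12.4.4 sets no age cut-points and Baseline age is already collected. The continuous term assumes a linear age effect on the log-odds scale, which can be checked with a spline. Merging will not make the older-patient estimate precise. At the top of the assumed range the merged band holds about 24 + 5 = 29 patients, for which the same formula gives a CI factor of exp(1.96·√(8.762/14.5)) = 4.6. The change should be recorded before treatment-effect results are seen.

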8.3.1.7 High sensitive Quick C-reactive protein test/ high sensitive C-reactive protein test

This assessment will be performed in order to identify the presence of inflammation, to determine its severity, and to monitor response to treatment. The quick hsCRP assessments will be performed locally at the study centers using a centrally provided assessment kit. The result of the quick hsCRP will be used to confirm eligibility of the patient (ASDAS ≥ 2.1 or CRP > 5 mg/L) at Screening and Baseline or to estimate further treatment of patients in the T2T arm at the Week 12 or Week 24 visit. In addition, the hsCRP assessment will be performed centrally as indicated in [Table 8-1](#) and used in final data analyses only.

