8.3.2 Ankylosing spondylitis disease activity score

The ASDAS is a composite index to assess disease activity in AS ([Lukas et al 2009](#), [Sieper et al 2009](#), [Machado et al 2011](#), [Machado et al 2018](#)). The ASDAS-ESR and ASDAS-CRP will be utilized to assess the disease activity status. Parameters used for the ASDAS include spinal pain (BASDAI question 2), the patient's global assessment of disease activity, peripheral pain/swelling (BASDAI question 3), duration of morning stiffness (BASDAI question 6) and CRP in mg/L (or ESR).

Disease activity states are inactive disease, low disease activity, high disease activity, and very high disease activity. The 3 values selected to separate these states were < 1.3 between inactive disease and low disease activity, < 2.1 between low disease activity and high disease activity, and > 3.5 between high disease activity and very high disease activity. Selected cutoffs for improvement scores were a change of ≥ 1.1 unit for "minimal clinically important improvement" and a change of ≥ 2.0 units for "major improvement" ([Machado et al 2011](#), [Machado et al 2018](#)).

ASDAS will be assessed by the investigator via eCRF at Screening and Baseline for all patients in order to estimate the eligibility of the patient. Only patients with ASDAS ≥ 2.1 can be considered to be enrolled into the study.

In addition, for patients in T2T arm the ASDAS will be calculated via eCRF at week 12 and week 24 in order to estimate the response and to decide further treatment.

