2.7.1.6 AS disease activity score

The ASDAS-CRP (based on Quick-CRP) and ASDAS-ESR (Ankylosing Spondylitis Disease Activity Score) will be utilized to assess the disease activity status. Parameters used for the ASDAS include: total back pain (BASDAI question 2), the patient global assessment of disease activity (ASAS component 1), peripheral pain/swelling (BASDAI question 3), duration of morning stiffness (BASDAI question 6) and C-reactive protein (CRP) in mg/liter (or ESR) (Sieper et al 2009, Lukas et al 2009).

The ASDAS formulas are as follows:

$$\text{ASDAS-CRP/ ASDAS-quick CRP} = 0.121 \times \text{total back pain} + 0.110 \times \text{patient global} + 0.073 \times \text{peripheral pain/swelling} + 0.058 \times \text{duration of morning stiffness} + 0.579 \times \ln(\text{CRP} + 1).$$
$$\text{ASDAS-ESR} = 0.113 \times \text{patient global} + 0.293 \times \sqrt{\text{ESR}} + 0.086 \times \text{peripheral pain/swelling} + 0.069 \times \text{duration of morning stiffness} + 0.079 \times \text{total back pain}.$$

CRP is in mg/liter, ESR is in mm/h; the range of other variables is from 0 to 10; \ln represents the natural logarithm; \sqrt represents the square root. If any of the ASDAS components are missing ASDAS will not be calculated.

ASDAS (CRP) will be assessed by the investigator via eCRF at screening and Baseline for all patients in order to estimate the eligibility of the patient. Only patients with ASDAS > 2.1 will be enrolled. In addition, the ASDAS will be calculated via eCRF at Week 12 and Week 24 in order to estimate the response and to decide further treatment. Locally assessed quick CRP values will be used in order to evaluate disease activity for these purposes.

Disease activity states are inactive disease, low disease activity, high disease activity, and very high disease activity. The 3 values selected to separate these states were < 1.3 between inactive disease and low disease activity, < 2.1 between low disease activity and high disease activity, and > 3.5 between high disease activity and very high disease activity. Selected cutoffs for

improvement scores were a change of ≥ 1.1 unit for “minimal clinically important improvement” and a change of ≥ 2.0 units for “major improvement” ([Machado et al 2011](#), [Machado et al 2018](#)).

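### The Baseline ASDAS subgroup is cut at 1.3 and 2.1, but eligibility requires at least 2.1, so the top class is almost the whole trial and the subgroup tells nothing

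*SAP*

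**What the plan says.** SAP 2.2.1 states that "Subgroup analyses for the primary efficacy endpoint will be performed on the following" and includes "Disease severity based on ASDAS at Baseline" in the list. The three classes are below 1.3, 1.3 to below 2.1, and 2.1 or above. SAP 2.5.4 repeats "disease severity based on ASDAS" with the same limits and adds an option: "The primary model may also be recalculated with these factors included", with subgroup-by-treatment terms. Protocol 12.4.4 names disease severity as a possible effect modifier but gives no cut-offs, so the limits are the SAP's own.

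On eligibility, criterion 4 in Protocol 5.1 requires ASDAS of at least 2.1 "at Screening and Baseline despite concurrent NSAID therapy" (or with NSAID intolerance or contraindication). Protocol 8.3.2 repeats that only such patients "can be considered to be enrolled into the study". SAP 2.7.1.6 gives the same floor, written as a strict inequality, and says of the eligibility and treatment decisions: "Locally assessed quick CRP values will be used in order to evaluate disease activity for these purposes".

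The same SAP section defines an ASDAS-CRP based on quick CRP and an ASDAS-ESR, and lists 3.5 as the boundary between high and very high activity. Protocol 8.3.1.7 adds that central hsCRP is "used in final data analyses only". Neither SAP 2.2.1 nor 2.5.4 says which ASDAS version defines the subgroup.

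**The concern.** The limits 1.3 and 2.1 separate the states a patient may reach after treatment. At Baseline both lie at or below the entry floor, so the top class coincides with the eligible range and the two lower classes hold only values that eligibility rules out. A lower class made up of eligibility deviations, or of patients who change side because a different ASDAS version is used, does not measure disease severity.

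At stake is one planned supportive analysis. Its table would duplicate the overall result under a severity label and could be misread as consistency across severity. If the optional interaction model is fitted, its ASDAS term is either not estimable or rests on a handful of patients. The effect-modification check by severity that Protocol 12.4.4 names would in practice not be done.

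**Working it through.** **Inputs from the documents.** Eligibility floor 2.1 (Protocol 5.1 and 8.3.2; SAP 2.7.1.6). Class limits 1.3 and 2.1 (SAP 2.2.1 and 2.5.4). State boundary 3.5 and the ASDAS formulas (SAP 2.7.1.6). ASAS40 of 50% with T2T and 30% with SOC, and 300 patients at 150 per arm (SAP 3). The documents give no Baseline ASDAS distribution, so every share below is an assumption.

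**1. The plan's own figure.** No stated number is in dispute, but the planning rates are reused, so they were checked first. Uncorrected n = [1.96·√(2·0.4·0.6) + 1.282·√(0.25 + 0.21)]² / 0.2² = 124. With continuity correction, (124/4)·[1 + √(1 + 4/(124·0.2))]² = 133.8, so 134 per arm, as stated. The odds ratio is (0.5/0.5)/(0.3/0.7) = 2.33, which the SAP rounds to 2.3.

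**2. Limits against the floor.**

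| Class | Overlap with ASDAS ≥ 2.1 | Expected, of 300 |
|---|---|---|
| < 1.3 | none | 0 |
| 1.3 to < 2.1 | none | 0 |
| ≥ 2.1 | all | 300 |

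This step needs no assumption beyond compliance with criterion 4 and use of the same ASDAS version.

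**3. Does the version matter?** Take assumed values: back pain 4, patient global 4, peripheral pain 0, stiffness 3, CRP 5 mg/L, ESR 8 mm/h.
- ASDAS-CRP = 0.121·4 + 0.110·4 + 0 + 0.058·3 + 0.579·ln(6) = 0.484 + 0.440 + 0.174 + 1.037 = 2.14
- ASDAS-ESR = 0.113·4 + 0.293·√8 + 0 + 0.069·3 + 0.079·4 = 0.452 + 0.829 + 0.207 + 0.316 = 1.80

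This patient meets the ASDAS floor and yet scores below 2.1 on ASDAS-ESR. (At CRP exactly 5 mg/L, criterion 5 would also need a positive MRI.) A patient can therefore fall in a lower class without any deviation if another version is used.

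**4. How closely the top class repeats the overall result.** Suppose 6 of 300 (2%, 3 per arm) fall below 2.1 and have no treatment effect. T2T response is then (147·0.5 + 3·0.3)/150 = 0.496, and the overall odds ratio is (0.496/0.504)/(0.3/0.7) = 2.30, against 2.33 in the top class.

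**5. Whether the lower class gives an estimate.** With m patients in each arm of the lower class at the planned rates, the chance that at least one arm is all responders or all non-responders (no finite odds ratio) is 1 − (1 − 0.3^m − 0.7^m)(1 − 2·0.5^m).
- m = 2 (4 patients): 1 − 0.42·0.50 = 0.79
- m = 3 (6 patients): 1 − 0.63·0.75 = 0.53
- m = 5 (10 patients): 1 − 0.8295·0.9375 = 0.22

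**6. What a cut at 3.5 could detect.** The variance of the log ratio of odds ratios is the sum of 1/(n·p·(1−p)) over the four arm-by-class cells, with p = 0.5 and 0.3 in both classes. The detectable ratio at 80% power is exp[(1.96 + 0.842)·SE].

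| Share in one class | Per arm | SE² | SE | Detectable ratio |
|---|---|---|---|---|
| 50% | 75 / 75 | 0.117 + 0.117 | 0.483 | 3.9 |
| 30% (or 70%) | 45 / 105 | 0.195 + 0.083 | 0.527 | 4.4 |
| 20% (or 80%) | 30 / 120 | 0.292 + 0.073 | 0.604 | 5.4 |

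These figures are unadjusted and assume no dropout.

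**The case against.** The strongest case for leaving the text alone is that little depends on it. This is one of four exploratory subgroups, with no alpha and no decision rule, and the interaction model is optional. SAP 2.7.1.6 already tabulates patients by ASDAS state at Baseline, so a reader would see the empty classes. Even after repair, the contrast detects only a ratio of odds ratios near 4 or more, against a planned overall odds ratio of 2.3. All of that is true and limits the weight of the point. It does not make the classes usable.

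Protocol 8.3.1.7 describes the quick test as confirming eligibility by ASDAS of at least 2.1 or CRP above 5 mg/L. Read alone, that would admit a patient below 2.1. Assumed values of CRP 6, back pain 3, patient global 3, peripheral pain 0 and stiffness 2 give ASDAS-CRP 0.363 + 0.330 + 0 + 0.116 + 1.127 = 1.94. But Protocol 5.1 requires all inclusion criteria and 8.3.2 repeats the floor, so the looser wording does not govern. The passages should be reconciled.

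The figures are simplified. Step 5 assumes an equal split between arms. With a random 1:1 split, counting an arm of 0 or 1 patient as uniform, the chances rise to 92%, 68% and 31%. Step 6 assumes no interaction when computing the variance. Holding SOC at 30% in both classes and T2T at 50% overall while an interaction exists gives about 4.0, 4.8 and 6.8. Center, a factor in the primary model, is ignored. The first correction makes the present classes look worse; the second makes the repair look weaker. Neither rescues the present limits.

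Finally, if ASDAS-ESR were meant, the number below 2.1 is unknown and could exceed a handful. That is a reason to name the version. It is not support for cuts at 1.3 and 2.1.

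**Conclusion.** The concern holds. On the quick-CRP ASDAS that SAP 2.7.1.6 uses for both eligibility and ASDAS-CRP, 0 of 300 patients are expected in the two lower classes, and the top class is the FAS. The FAS keeps all randomized patients, so deviations can put a few below 2.1. Even at an assumed 2%, the top class is 98% of the FAS. That conclusion rests on criterion 4 being applied as written and on the eligibility version defining the subgroup, which the SAP leaves unstated.

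The consequence is confined to this subgroup and its optional interaction term. It should be corrected because the SAP commits to the analysis and the repair is trivial. The trial's main conclusion does not depend on it.

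**What to change.** In SAP 2.2.1 and 2.5.4, replace the three classes with two, split at the existing 3.5 boundary: 3.5 or below (high activity for eligible patients) and above 3.5 (very high). State that Baseline ASDAS-CRP from local quick CRP defines them. Count any FAS patient below 2.1 in the lower class, so that nobody is dropped, and report how many there are. Use this two-level factor if the interaction model is fitted.

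Because the trial is open-label, fix the cut before outcomes are examined by stratum, or label it post hoc. Label the analysis exploratory in either case. The share above 3.5 is not given in the documents, so a balanced split cannot be promised. A continuous Baseline ASDAS-by-treatment term is a sensible optional addition that avoids choosing a cut.

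The cost is one line in each of two SAP sections and one sentence naming the version. It needs no new data and does not touch the primary analysis. The same edit could reconcile the strict and non-strict forms of the 2.1 floor between SAP 2.7.1.6 and the protocol.
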